## **2. Subject Selection**

**Inclusion Criteria:** The study involves males and females aged  $\geq 21$  years who are English and Spanish-speaking patients at a Piedmont Health Services primary care health center; and with a BMI between 25-40 kg/m^2 and weight less than 380 pounds. Eligible participants will have had a non-urgent visit to a Piedmont Health clinic within the last 2 weeks. Eligible participants will also have a cell phone and be willing to receive study-related text messages (3-12 messages per week).

**Exclusion Criteria:** Potential participants cannot: be a current Piedmont Health employee; currently or recently (within the past six months) pregnant or planning on becoming pregnant in the next 12 months; be currently or recently (past 2 months) lactating; have prior or planned bariatric surgery; have a diagnosis contraindicating weight loss (e.g., active malignancy); have a history of a cardiovascular event (stroke, MI); or have been hospitalized for a mental health issue in the last 12 months; have a diagnosis of end-stage kidney disease (ESRD) in the medical record; or due to investigator discretion for a potential health or safety issue. Potential participants who have a history of a coronary artery revascularization (in last 12 months) will be allowed to participate in the study with provider approval (See Appendix C).

**Sample size:** We will recruit up to 455 adult men and women, who speak either English or Spanish. At least 30% of the sample will be male (we recently recruited a 31% male sample in Track). The sample size calculation is based on the primary aim examining differences in the time to gain  $\geq 3\%$  of baseline weight between intervention and control groups. Based on Shape's clinical data, we assume a 5% sample loss for each group per month of the study. A sample of N=192 per group (Total N=384) allows us to test the difference between the two distributions with greater than 80% power. Factoring in an additional expected sample loss of 15% (those with no clinical data past baseline) gives a final sample size of N=221 per group (Total N=442, with the possibility of enrolling up to 455).

For the qualitative Balance implementation sub-study, we will recruit up to 25 Piedmont Health employees in varying roles and across the participating sites and leadership team.

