For both recruitment methods, we will screen participants, consent those to Balance who meet eligibility criteria over the phone or in-person in the clinic, and conduct survey and randomization activities as outlined above in the Data Collection section: Baseline Assessment. Study surveys will eliminate or define medical terms and use simple sentence structure and vocabulary. As in previous trials we will offer all recruitment, enrollment, and assessment activities in both English and Spanish in order to maximize the representativeness of the study sample. For both recruitment methods, we will reach out to potential participants via phone call, text message and/or email to assess interest in the study, and if interested, for phone screening, consent and enrollment.

We will randomize participants in permuted blocks, stratified by health center to balance assignment by community health center. With our design, research staff and participants cannot reasonably be blinded to allocation. However, to reduce the potential for biased outcomes, we take steps to segregate research staff from those involved in intervention design and evaluation. Our work demonstrates the feasibility of this methodology; indeed, we designed this strategy together with Piedmont and they agree that it will be minimally burdensome to clinic operations.

Patients who sign the HIPAA authorization form but are ineligible for the study based on screen will be informed they are not eligible for Balance. If the only reason a participant is ineligible for the study is too high based on BMI/weight from their chart (i.e. BMI was above 40 kg/m^2; and/or weight was greater than 380 lbs), s/he will be mailed a cover letter; copy of health education materials based on the NHLBI's "Aim for a Healthy Weight" booklet; and a printed copy of an IRB-approved Charge study recruitment

flyer (Duke Campus IRB Protocol Number D0752) with information about how to sign up for that trial, if interested (for English-speakers only), during the time that Charge is actively recruiting. (See Appendix C for eligibility screen).

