## **STATISTICAL ANALYSIS PLAN**

## Statistical Analysis Plan

Baseline variables were summarized by the intervention arm as means and SDs for continuous variables and as counts and percentages for categorical variables. We used a 2-stage modeling strategy to answer our primary hypothesis. All analyses were intent-to-treat. For the first stage, we estimated the intervention effect on weight using a constrained longitudinal linear mixed effects model, using all available data from between 18 months pre-enrollment through 30.5 months postenrollment. We explored nonlinearities for the fixed effects of time and random effects of time in the models, guided by the Bayesian Information Criterion and likelihood ratio tests. The model included fixed effects for time and interactions between time segments and intervention, with a random intercept and random slopes for time. The covariance between random effects was modeled using an unstructured covariance matrix. Randomization was stratified by CHC; thus, we adjusted for CHC in the analyses but did not adjust for other variables. Using this linear mixed effects model, we estimated mean weight change by intervention arm, and the difference between intervention arms in mean weight change, at 6, 12, 18, and 24 months.

Second, we compared the percentage of  $\leq 3\%$  weight gain, our primary outcome, in each arm at 24- months postrandomization using individual empirical best linear unbiased predictors (EBLUPs) from the mixed model. To ensure good predictions, we only used individual EBLUPs from participants with at least 1 EHR weight documented within a 6-month window centered on the 24-month time point (ie, between 21 and 27 months postenrollment). We compared the percentage of  $\leq 3\%$  weight gain in intervention and usual care arms using both a log-binomial model and linear risk model on the EBLUP output, in order to obtain both risk ratios and risk differences, which provide estimates of relative and absolute efficacy, respectively. The extra variability induced by the EBLUPs being predicted from the model was taken into account using a resampling procedure, explained further in the Multimedia Appendices 1 and 2. Sensitivity to the 21- to 27-month window was assessed by obtaining predictions after expanding the window. We additionally used EBLUPs to compare the percentage of  $\leq 3\%$  weight gain in each arm at 6-, 12-, and 18-months postrandomization.

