Additional sensitivity analyses included adjusting the model for baseline variables imbalanced across arms, by weight measured in the primary time window ( $P < .10$ ) and removing telehealth visits from the analysis. We also explored effect modification by adding interactions to the primary model with age tertiles; gender; BMI class; race and ethnicity; and preferred language (English or Spanish), each in a separate model. Additionally, in post hoc analyses we added the completion date of the study (pre- or post-COVID) as an effect modifier to examine the potential impact of COVID-19 on the intervention effect.

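### The only sensitivity analysis that adds baseline covariates picks them by a P<.10 imbalance rule tied to the 21-27 month weight subset, not by prognosis; a fixed list would be a better and cheap check

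*Combined protocol and SAP*

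**What the plan says.** The first stage of the SAP is a mixed model: "we estimated the intervention effect on weight using a constrained longitudinal linear mixed effects model". Beyond the time and time-by-arm terms it contains health center only: "thus, we adjusted for CHC in the analyses but did not adjust for other variables". This follows the randomization described in the protocol, Section 2 (Recruitment): "We will randomize participants in permuted blocks, stratified by health center to balance assignment by community health center". The second stage, which compares the proportions with at most 3% gain, is limited to participants seen near 24 months: "we only used individual EBLUPs from participants with at least 1 EHR weight documented within a 6-month window", running from 21 to 27 months.

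The final paragraph of the SAP lists one sensitivity analysis that brings in other baseline covariates: "adjusting the model for baseline variables imbalanced across arms, by weight measured in the primary time window". The threshold follows in the same sentence: "by weight measured in the primary time window ( $P < .10$ ) and removing telehealth visits from the analysis". The SAP does not name the candidate variables or the test, and does not say whether the covariates enter as main effects or also interact with time.

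The other sensitivity analyses (a wider window, exclusion of telehealth visits) change which data are used and add no covariates. Age tertiles, gender, BMI class, race and ethnicity, and preferred language appear only as effect modifiers, each in its own model.

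**The concern.** A covariate is worth adjusting for when it predicts the outcome or the chance of observing it. A rule based on the P value of a baseline difference tests neither. A strongly prognostic variable with P=.15 is left out, and an irrelevant one with P=.08 goes in. The set is fixed only after the data are seen.

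The analysis being checked uses a subset defined after randomization, those with a 21-27 month weight. Read as imbalance across arms, the rule cannot flag a variable that predicts having a window weight equally in both arms, although such a variable bears on whether the missing weights can be ignored. If nothing is flagged, the sensitivity analysis is the primary analysis run again. Readers may then take the agreement as evidence of robustness when nothing was tested.

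**Working it through.** **Inputs.** The documents give no figure for this analysis. From the protocol, Section 2 (Sample size): 192 per group, inflated by 15%. 192 × 1.15 = 220.8, rounded up to 221 per group, which reproduces the stated 442 in total. This serves only as a sample size below. The number of candidate variables, their correlation ρ with the outcome and the variance they explain (R²) are not in the documents; they are assumptions, shown over ranges.

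**1. How often the rule flags something.** For k independent variables in the full randomized sample, P(at least one flag) = 1 − 0.9^k.
- k = 5: 41%
- k = 10: 65%
- k = 15: 79%
- k = 20: 88%

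The complement is the chance that the check simply repeats the primary analysis: 59% at k = 5 and 35% at k = 10. If three of the candidates are prognostic, the chance that none of the three is selected is 0.9³ = 73%.

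**2. Width against the unadjusted analysis.** For one covariate, the ratio of adjusted to unadjusted standard error (SE) is √(1 − ρ²) / √(1 − r²), with r² = t²/(t² + N − 2). At N = 442 and an imbalance of exactly P=.10, 1/√(1 − r²) = 1.003. The ratio is then:
- ρ = 0: 1.003
- ρ = 0.1: 0.998
- ρ = 0.3: 0.957
- ρ = 0.5: 0.869
- ρ = 0.7: 0.716

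Adjustment widens the interval only if ρ is below about 0.08, and then by about 0.3%.

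**3. Selection against a fixed list, single-outcome regression.** Simulation with N = 300 and 10 variables, 3 of them prognostic:

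| R² | SE, P<.10 rule | SE, fixed list | Power, rule | Power, fixed list |
|---|---|---|---|---|
| 2% | 0.1163 | 0.1163 | 76.4% | 76.8% |
| 5% | 0.1160 | 0.1144 | 76.5% | 77.5% |
| 15% | 0.115 | 0.108 | 75% | 79% |
| 25% | 0.115 | 0.102 | 74% | 83% |

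At R² = 0 the fixed list is slightly worse (74.1% against 74.9%). Unadjusted and rule-based SEs are almost the same: 0.1154 and 0.1154 at 15%, 0.1153 and 0.1146 at 25%.

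**4. The same question in a constrained mixed model** (N = 300, assumed variances). Covariates entered as main effects leave the SE of the arm-by-time effect at 0.365. A fixed list with covariate-by-time terms lowers it to 0.343 at a slope R² of 15% and 0.325 at 25%, with almost no gain at 2% to 5%. The loss from not using the list is 0.365/0.343 = 1.06 and 0.365/0.325 = 1.12. How the covariates enter therefore matters as much as which ones are chosen.

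**The case against.** The case for leaving the plan alone has real content.

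- **It is one sensitivity analysis.** The primary estimate adjusts for health center whatever the imbalance, so its inference is untouched. This stands.
- **When a prognostic covariate is flagged, adjusting for it is right.** Given a flag, the adjusted test kept its size in simulation (4.7% to 5.3% for ρ from 0 to 0.7), while the unadjusted test reached 8.4%, 15.3% and 25.7% at ρ = 0.3, 0.5 and 0.7. This stands, but it says nothing about the variables that the rule leaves out.
- **The gain from a fixed list may be small.** The model already uses repeated weights from 18 months before enrollment, with random intercepts and slopes. What demographics add to weight change is unknown. This stands as a limit on size.
- **The sentence may mean imbalance by whether a window weight was measured.** On that reading the rule could pick up predictors of attendance, and that part of the criticism falls away. The dependence on the data does not.
- **Selective follow-up is handled elsewhere.** Stage 1 uses all available data and the window is widened. True, but neither step conditions on baseline covariates.

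A reader might infer that the P<.10 rule makes this a wider, conservative check. The documents do not say so, and the working does not show it: the rule-based SE is about the same as the unadjusted one. Taken alone, an adjust-only-if-flagged test does have overall size below 5% (4.7%, 4.1% and 3.3% at ρ = 0.3, 0.5 and 0.7), but the primary result is not produced by that rule. A reader might also infer that flags arise purely by chance. That is exact only for the full randomized sample; among participants with a window weight, imbalance can also reflect differential attendance.

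**Conclusion.** The criticism of the selection rule holds; its consequence is modest. The plan's only sensitivity analysis with added baseline covariates uses a data-dependent set chosen without regard to prognosis, and it may be empty. Agreement with the primary result is therefore weak evidence of robustness. Against a fixed prognostic list the SE is about 6% to 12% larger if the covariates explain 15% to 25% of the variance in weight change, and negligibly different at 2% to 5%.

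These sizes rest on assumed R², variable counts and variance components. The second-stage comparison of predicted weights was not simulated. The SAP's Multimedia Appendices 1 and 2, cited for the resampling procedure, were not available. Minor severity; a cheap improvement.

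**What to change.** Delete the P<.10 rule. Fit the sensitivity model with a fixed list regardless of observed imbalance: age, gender, baseline BMI class, race/ethnicity and preferred language, all already named in the SAP as effect modifiers. Enter each as a main effect and as a covariate-by-time term, so that it acts on weight change and so that the missing-at-random assumption for the 24-month weight is conditional on it. Main effects alone would change almost nothing.

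Report baseline standardized differences descriptively, by arm and by presence of a 21-27 month weight. This covers both readings of the present sentence without a test.

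The SAP is written in the past tense. If the analysis has been run, report the fixed-list model as added, not as prespecified, and state which variables the P<.10 rule selected and in which sample.

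The cost is one SAP sentence, one further model fit on data already planned for collection, and a few more parameters. The gain will be small if the covariates are weakly prognostic. The second stage would still be limited to participants with a window weight.

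### Effect modification by age and BMI is explored only through age tertiles and BMI class, which loses power against a graded modifier; continuous interactions are a cheap addition

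*Combined protocol and SAP*

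**What the plan says.** The last paragraph of the Statistical Analysis Plan states: "We also explored effect modification by adding interactions to the primary model". The modifiers are listed in the same sentence: "adding interactions to the primary model with age tertiles; gender; BMI class; race and ethnicity", followed by preferred language, one model each. The plan describes no interaction with age or BMI as a continuous variable. It gives no BMI cut-points, number of BMI classes, form of test, degrees of freedom, alpha or power for these analyses.

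The model being extended is the linear mixed model of weight: "The model included fixed effects for time and interactions between time segments and intervention". The number of time segments is not given.

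Both variables exist as numbers. In section 2 (Subject Selection), eligibility is set by a numeric age limit of 21 years and "with a BMI between 25-40" kg/m². The recruitment text there has date of birth entered in the study database and uses the last recorded BMI and weight from the health record.

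The only power statement, under Sample size in section 2, belongs to another question: "The sample size calculation is based on the primary aim examining differences in the time to gain" at least 3% of baseline weight. For that aim, "A sample of N=192 per group (Total N=384) allows us to test the difference between the two distributions with greater than 80% power".

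**The concern.** Cutting a continuous modifier into groups discards its variation within groups. With three unordered groups, the interaction also costs two degrees of freedom per time contrast where a continuous term costs one. If the effect rises or falls steadily with age or BMI, both features make the test less likely to find it.

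The practical risk is one of interpretation. A null exploratory result could be read as an effect that is uniform across age and BMI when the grouped test was likely to miss a gradient. The trial was sized for the primary comparison only, with substantial data loss expected ("we assume a 5% sample loss for each group per month of the study", plus a further 15% with no clinical data after baseline). Power for interactions was not planned for, so a loss that can be avoided at little cost is worth avoiding. Age tertiles also depend on the enrolled sample, which makes comparison with other studies harder.

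**Working it through.** **The plan's own figure.** The documents give no power for any interaction, so there is nothing to reproduce on this point. The stated power above 80% for the primary aim cannot be reproduced either, because no hazard ratio, event rate, alpha or sidedness is given. It is not used below.

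**Assumptions, none from the documents.**
- Two-sided alpha 0.05.
- A modifier whose effect is linear.
- As benchmark, a trend just large enough for a continuous 1-df interaction to have 80% power.
- The age and BMI distributions named below.

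**Method.** Power is P(χ²(df, λ) > critical value), with λ the noncentrality. Grouping multiplies λ by R², the share of the modifier's variance that lies between groups. An unordered test on k groups has k − 1 df.

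**Continuous term.** Power of 80% on 1 df requires λ = 7.849.

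**Age tertiles, normal age.** The tertile means are −1.091, 0 and +1.091 SD, so R² = (2/3) × 1.091² = 0.793. Then λ = 7.849 × 0.793 = 6.22. On 2 df (critical value 5.99), power is **60.1%**.

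**Other age distributions, same 2-df test.**

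| Assumed age distribution | R² | Power |
|---|---|---|
| Normal (mean 48, SD 13) truncated at 21 | 0.809 | 61.0% |
| Uniform | 0.889 | 65.4% |
| Right-skewed (21 + gamma, shape 2, scale 12) | 0.716 | 55.5% |

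**Tertiles scored as a 1-df trend.** Power is 70% for normal age and 65-75% across the same distributions.

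**BMI class.** The plan gives neither the cut-points nor the number of classes, so two readings were tried on the 25-40 range. The distributions were truncated normal (means 31 to 33 with SD 4, and mean 32 with SD 5) and uniform.

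| Assumed classes | df | R² | Power |
|---|---|---|---|
| Three (cuts at 30 and 35) | 2 | 0.832-0.889 | 62-65% |
| Two (cut at 30) | 1 | 0.533-0.667 | 53-63% |

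**Several time segments.** If the modifier is tested jointly over two or three segments, starting again from 80% for the continuous version, the grouped test has 57-64% (R² from 0.793 to 0.889).

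**Other starting points.** For normal age in tertiles on 2 df, 90% falls to 74%, 50% to 33%, and 30% to 19%.

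**What the remedy gives up.**
- If a linear and a spline term are tested jointly on 2 df, λ = 7.849 gives 71%. That returns (80 − 71)/(80 − 60) = 9/20 of the gain, about half.
- If the effect instead steps at the upper tertile, a 2-df tertile test with 80% power has λ = 9.635. The squared correlation of a normal modifier with that step is 0.595, so the linear term has λ = 9.635 × 0.595 = 5.73 and power of about 67%.

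**The case against.** The strongest reply is that this is a reasonable choice for an exploratory analysis. Categories are easy to read, can show non-monotone patterns, and assume no straight line. The comparison above takes as true the linear form for which a continuous term is best. Under a step at the upper tertile the ordering reverses (80% for tertiles, about 67% for the linear term). If only the middle tertile differed, symmetrically, a linear term would have almost no power. All of this stands. It is why the point is an addition to the plan and why the grouped estimates should stay.

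A reader might also draw stronger conclusions that the documents do not support:

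- **That this trial's interaction power falls from 80% to 60%.** The 80% here is a chosen benchmark. The plan's own figure above 80% concerns time to weight gain, and no interaction effect size, alpha or covariate distribution is given.
- **That the trial in effect uses about 285 of its 442 participants.** The sample multiplier for equal power at the benchmark is 9.635/6.22 = 1.55, and 442/1.55 is 285. But 442 is an enrolment target before planned losses, and the ratio depends on the same unstated test and assumed age distribution.
- **That BMI is cut into three groups.** The plan says only BMI class; overweight against obese fits the text as well.
- **That the result decides who is offered the programme.** No passage ties such a decision to these tests.

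**Conclusion.** The point holds as a minor one. The plan explores age and BMI only in categories, and against a roughly linear modifier every scenario examined loses power. From an 80% benchmark, unordered age tertiles have about 60% (55-65% across assumed age distributions), or about 70% if scored as a trend. BMI class has about 53-65%.

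These figures rest on an assumed two-sided alpha of 0.05, a linear trend and assumed distributions. They also depend on choices the plan leaves open: the form of the test, the BMI classes and the number of time segments. They illustrate the relative cost of grouping and do not estimate this trial's power. The mixed model, the 24-month comparison of weight gain of at most 3%, and the primary conclusion are unaffected.

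**What to change.** In the exploratory effect-modification analysis, base the age and BMI tests on the interaction of intervention-by-time with continuous age and with continuous BMI, at 1 df per time contrast. Add a spline term as a secondary check of linearity, reported separately from the main test. Keep the tertile and BMI-class estimates for display, and state the tertile boundaries, the BMI cut-points and the number of classes.

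The cost is a short change of wording and a rerun of two exploratory models on data already held. The downside is that the main test then assumes linearity and would be weaker for a step or non-monotone pattern; testing the spline jointly with the linear term gives back about half of the gain.
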